risk factor for severe COVID-19 and a positive SARS-CoV-2 RT-qPCR test at baseline), and that 83% of randomized patients will have a positive SARS-CoV-2 RT-qPCR test at baseline.

Table 12 presents estimated number of randomized patients with at least 1 risk factor for severe COVID-19 at each analysis time point for cohort 1 efficacy analysis.

Table 12: Estimated Sample Sizes at Each Analysis Time Point for Phase 3 Patients with ≥1 Risk Factor for Severe COVID-19

	Placebo	1200 mg	2400 mg	8000 mg	Total
	FAS (mFAS) ¹				
Pre-Amendment 6 patients	662 (550)	Not	662 (550)	662 (550)	1986 (1650)
		applicable			
Amendment 6/7 randomized by	841 (698)	841 (698)	841 (698)	N/A	2523 (2094)
17 January 2021					
Final analysis, 2400 mg vs.	1503 (1248)		1503 (1248)		
placebo (randomized by 17					
January 2021)					
Interim analysis, 1200 mg vs.	841 (698)	841 (698)			
placebo (randomized by 17					
January 2021)					
Amendment 6/7 randomized by	1352 (1122)	1352 (1122)	1352 (1122)	N/A	4056 (3366)
24 February 2021					
Final analysis, 1200 mg vs.	1352 (1122)	1352 (1122)			
placebo (randomized by 24					
February 2021)					

¹ FAS estimates only include those in FAS with ≥1 risk factor for severe COVID-19.

The final primary efficacy analysis for the 2400 mg dose group versus placebo comparison will be performed based on patients randomized on or before 17 January 2021, which includes approximately 1503 randomized patients with COVID-19 risk factors per group in the 2400 mg dose group and the placebo group (1248 per group in the mFAS). With this sample size, the study will have approximately 76% power to detect a significant treatment effect in the proportion of patients with \geq 1 COVID-19-related hospitalization or all-cause death in mFAS at a 2-sided α of 0.05, assuming 3.4% of patients in the placebo group and 1.7% of patients in the 2400 mg group have an event (ie, a 50% reduction with REGN10933+REGN10987 treatment). If there is a greater treatment difference, such as a 60% reduction, the study will have at least 90% power to detect a significant treatment effect in the proportion of patients with \geq 1 COVID-19-related hospitalization or all-cause death.

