9	Proportion of patients with MAVs through day 29 in the mFAS for REGN10933+REGN10987 2400 mg and 8000 mg combined group versus placebo (patients 1 through 799)	
10	Proportion of patients with subset of MAVs consisting only of hospitalization or ER visit or urgent care visit through day 29 in the mFAS for REGN10933+REGN10987 2400 mg and 8000 mg combined group versus placebo (patients 1 through 799)	

Phase 3

Cohort 1

The primary endpoint and key secondary endpoint will be tested hierarchically (Table 14), adjusting for interim analysis as described below.

Table 14: Statistical Testing Hierarchy, Phase 3 Cohort 1 Analysis

Hierarchy Number	Description	
1	Proportion of patients with ≥1 COVID-19-related hospitalization or all-cause death through day 29 in the mFAS for REGN10933+REGN10987 2400 mg group versus placebo	
2	Proportion of patients with ≥1 COVID-19-related hospitalization or all-cause death through day 29 in the mFAS for REGN10933+REGN10987 1200 mg group versus placebo	
3	Proportion of patients with ≥1 COVID-19-related hospitalization or all-cause death through day 29 in the mFAS patients with baseline viral load >10 ⁶ copies/mL for REGN10933+REGN10987 2400 mg group versus placebo	
4	Proportion of patients with ≥1 COVID-19-related hospitalization or all-cause death through day 29 in the mFAS patients who are seronegative at baseline for REGN10933+REGN10987 2400 mg group versus placebo	

Hierarchy Number	Description	
5	Proportion of patients with ≥1 COVID-19-related hospitalization or all-cause death through day 29 in the mFAS patients with baseline viral load >10 ⁶ copies/mL for REGN10933+REGN10987 1200 mg group versus placebo	
6	Proportion of patients with ≥1 COVID-19-related hospitalization or all-cause death through day 29 in the mFAS patients who are seronegative at baseline for REGN10933+REGN10987 1200 mg group versus placebo	
7	Proportion of patients with ≥1 COVID-19-related hospitalization or all-cause death from day 4 through day 29 in the mFAS for REGN10933+REGN10987 2400 mg group versus placebo	
8	Proportion of patients with ≥1 COVID-19-related hospitalization or all-cause death from day 4 through day 29 in the mFAS for REGN10933+REGN10987 1200 mg group versus placebo	
9	Time to COVID-19 symptoms resolution in the mFAS for REGN10933+REGN10987 2400 mg group versus placebo	
10	Time to COVID-19 symptoms resolution in the mFAS for REGN10933+REGN10987 1200 mg group versus placebo	

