The final analysis of the primary efficacy endpoint, ie, proportion of patients with ≥ 1 COVID-19-related hospitalization or all-cause death through day 29 for the 2400 mg group versus placebo comparison will be performed based on patients randomized on or before 17 January 2021 in the mFAS, at α level of 0.05.

If the 2400 mg group versus placebo comparison for the primary endpoint is positive, an interim analysis of the primary efficacy endpoint for the 1200 mg group versus placebo comparison (2 in Table 14) will be performed at α level of 0.01 based on patients randomized on or before 17 January 2021 in the mFAS. If the comparison is positive, this analysis will be considered as the final analysis of the proportion of patients with \geq 1 COVID-19-related hospitalization or all-cause death through day 29 for the 1200 mg group versus placebo comparison. Final analysis of the primary and key endpoints for comparisons 3 to 10 (Table 14) will then be performed based on patients randomized on or before 17 January 2021 in the mFAS in the hierarchical order above at α level of 0.05.

If the interim analysis of the primary efficacy endpoint for the 1200 mg group versus placebo comparison is negative at α level of 0.01, no tests will be performed for the primary and key endpoints for comparisons 3 to 10 based on patients randomized on or before 17 January 2021. Final analysis of the proportion of patients with \geq 1 COVID-19-related hospitalization or all-cause death through day 29 for the 1200 mg group versus placebo comparison (2 in Table 14) and other comparisons 3 to 10 will be performed based on all patients randomized on or before 24 February 2021 and tested hierarchically at an alpha level adjusted based on the information fraction at the interim analysis using Gamma family alpha spending function, eg, at 0.047 level as illustrated in the example in Table 15.

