The phase 3 sample size of the study is based on having sufficient power to analyze the primary endpoint of proportion of patients with a COVID-19-related hospitalization or all-cause death in the modified full analysis set (mFAS). Based on data from the phase 2 analysis involving the first 799 symptomatic patients enrolled and blinded phase 3 data, the sponsor assumes an event rate of 3.4% for COVID-19-related hospitalization or all-cause death among patients on placebo in the mFAS (patients with at least 1 risk factor for severe COVID-19 and a positive SARS-CoV-2 RT-qPCR test at baseline), and that 83% of all randomized patients (FAS) will have a positive SARS-CoV-2 RT-qPCR test at baseline.

The following table presents estimated number of randomized patients with at least 1 risk factor for severe COVID-19 at each analysis time point for cohort 1 efficacy analysis.

	Placebo FAS ¹ (mFAS)	1200 mg FAS ¹ (mFAS)	2400 mg FAS ¹ (mFAS)	8000 mg FAS ¹ (mFAS)	Total FAS ¹ (mFAS)
Pre-Amendment 6 patients	662 (550)	Not applicable	662 (550)	662 (550)	1986 (1650)
Amendment 6/7 patients randomized by 17 January 2021	841 (698)	841 (698)	841 (698)	Not applicable	2523 (2094)
Final analysis for 2400 mg vs. placebo (patients randomized by 17 January 2021)	1503 (1248)		1503 (1248)		
Interim analysis for 1200 mg vs. placebo (patients randomized by 17 January 2021)	841 (698)	841 (698)			
Amendment 6/7 patients randomized by 24 February 2021	1352 (1122)	1352 (1122)	1352 (1122)	Not applicable	4056 (3366)
Final analysis for 1200 mg vs. placebo (patients randomized by 24 February 2021)	1352 (1122)	1352 (1122)			

Table 2:Estimated sample sizes at each analysis time point for Phase 3 patients with
at least 1 risk factor for severe COVID-19

¹FAS estimates only include those in FAS with ≥ 1 risk factor for severe COVID-19.

The final primary efficacy analysis for the 2400 mg dose group versus placebo comparison will be performed based on patients randomized on or before 17 January 2021, which includes approximately 1503 randomized patients with COVID-19 risk factors per group in the 2400 mg dose group and the placebo group (1248 per group in mFAS). The study will have approximately 76% power to detect a significant treatment effect in the proportion of patients with \geq 1 COVID-19-related hospitalization or all-cause death in mFAS at a 2-sided α of 0.05, assuming 3.4% of

CONFIDENTIAL

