3.1. Efficacy Analysis Sets

Cohort 1

All symptomatic patients from the 800th randomized symptomatic patient will be included in the phase 3 portion of the study. The full analysis set (FAS) includes all randomized patients in phase 3 cohort 1, including those with or without risk factors for severe COVID-19, and is based on the treatment allocated (as randomized).

The modified full analysis set (mFAS) for phase 3 includes all randomized patients with a positive central lab-determined RT-qPCR test from nasopharyngeal (NP) swab samples at randomization, and *with at least one risk factor for severe COVID-19 at baseline*. If pre-dose virologic results from the qualitative test are missing, then results from post-dose sample may be used to determine the qualitative PCR status at baseline, as long as the sample was collected within 2 hours after starting the study drug infusion. The mFAS is based on the treatment allocated (as randomized). The seronegative mFAS is defined as all randomized patients with documented seronegative status (eg, SARS-CoV-2 serum antibody negative) at baseline in the mFAS.

Both mFAS and FAS will be used for the summaries of demographic and baseline characteristics. The mFAS will be used for the analysis of clinical, symptoms, and virologic endpoints. The seronegative mFAS will be used for the analysis of certain virologic endpoints and in analyses of certain clinical endpoints. Data from patients with no risk factors will be summarized descriptively.

For the analyses of 1200 mg group comparing to placebo, only patients concurrently randomized (ie, after Protocol Amendment 6 is implemented) will be included.

Cohort 2

The FAS includes all randomized patients in phase 3 cohort 2 and is based on the treatment allocated (as randomized). The modified full analysis set (mFAS) includes all randomized patients with positive RT-qPCR in NP swab samples at randomization and is based on the treatment allocated (as randomized). If pre-dose results from the qualitative test are missing, then results from post-dose sample may be used to determine the qualitative PCR status at baseline, as long as the sample was collected within 2 hours after starting the study drug infusion. The seronegative mFAS is defined as all randomized patients with documented seronegative status at baseline in the mFAS.

Cohort 3

Data on all patients in Cohort 3 (pregnant population) will be utilized in the analyses.

CONFIDENTIAL

Page 18 of 61

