5.7. Analyses of Efficacy Variables

5.7.1. Analysis of Primary Efficacy Variables

Cohort 1

The primary efficacy analysis for the clinical endpoint, proportion of patients with COVID-19-related hospitalization or all-cause death through day 29, will be performed based on the mFAS.

The analyses of proportion of patients with COVID-19-related hospitalization or all-cause death through day 29 will be performed for the following null and alternative statistical hypotheses:

- H₀: The risk of having COVID-19-related hospitalization or all-cause death through day 29 for REGN10933+REGN10987 2400 mg group is the same as that for placebo
- H₁: The risk of having COVID-19-related hospitalization or all-cause death through day 29 for REGN10933+REGN10987 2400 mg group is not the same as that for placebo

The proportion of patients with COVID-19-related hospitalization or all-cause death through day 29 will be compared between each dose group and placebo using the stratified Cochran-Mantel-Haenszel (CMH) test with country as a stratification factor. P-values from the stratified CMH test and 95% confidence intervals for the risk ratio and relative risk reduction (1-risk ratio) using Farrington-Manning method will be presented. Exact method for p-values and confidence intervals

will be used if the expected frequencies in all cells are not at least 5. As key secondary analyses, the same analyses will be performed for the proportion of patients with COVID-19-related hospitalization or all-cause death through day 29 for patients with high baseline viral load (>10⁶ copies/mL) in the mFAS and for seronegative mFAS, and for proportion of patients with a COVID-19-related hospitalization or all-cause death from day 4 through day 29 in the mFAS. The comparison of 1200 mg dose group to placebo will include only the subset of placebo patients concurrently randomized with 1200 mg dose group. Sensitivity analyses will be performed using FAS. Additional subgroup analysis will also be performed by baseline serostatus (negative, positive, other) and by baseline viral load categories (>10⁴ copies/mL, >10⁵ copies/mL, >10⁶ copies/mL, >10⁶ copies/mL, >10⁷ copies/mL).

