proportion endpoints between 1200 mg and 2400 mg dose groups will calculated based on patients concurrently randomized, i.e., under Amendment 6, 7 or 8, for the mFAS.

Analyses will be performed for the cumulative incidence of patients having a COVID-19-related hospitalization or all-cause death through day 29 based on the time to first COVID-19-related hospitalization or all-cause death using the stratified log-rank test with randomization strata (country) as stratification factor for mFAS. Estimates of cumulative event rate at different time points and associated 95% confidence intervals using the Kaplan-Meier method will be reported. The hazard ratio and its 95% CI for patients having event will be estimated by the Cox regression model with terms for treatment group (2400 mg dose groups versus placebo), and randomization strata. The p-value from the stratified log-rank test for risk of having events will be reported. Similar analysis will be performed comparing 1200 mg dose group to placebo including only the subset of patients concurrently randomized. A patient who has no COVID-19-related hospitalization will be censored at last known date of contact up to day 29. A patient who dies on or before day 29 will be considered as having an event at the date of death. A patient with multiple COVID-19 related hospitalization visits and/or who dies will be counted as having one event with time computed at the first event.

Similar secondary analyses will be performed for cumulative incidence of patients having a COVID-19-related hospitalization, ER visit, or all-cause death and cumulative incidence of patients having a COVID-19-related MAV or all cause death through day 29 for the mFAS.

Additional landmark analysis for time to event endpoint such as cumulative incidence of hospitalization or death may be performed if the proportional hazard assumption is considered not valid.

Sensitivity analyses will be performed using FAS.

Additional analyses will be performed to examine the relationship between viral load and COVID-19-related MAVs in patients who underwent an intensive sampling schedule. Viral load over time will be compared between patients with and without a COVID-19-related MAV.

Cohort 2 and 3

Proportion of patients with COVID-19-related hospitalization or ER or urgent care visits or allcause death as well as proportions of patients with each type of MAVs for cohort 1 patients with no risk factor, cohort 2 and 3 will be descriptively summarized.

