The final analysis of the primary efficacy endpoint, i.e., proportion of patients with ≥ 1 COVID-19-related hospitalization or all-cause death through day 29 for the 2400 mg group versus placebo comparison will be performed based on patients randomized on or before 17 January 2021 in the mFAS, at α level of 0.05.

If the 2400 mg group versus placebo comparison for the primary endpoint is positive, an interim analysis of the primary efficacy endpoint for the 1200 mg group versus placebo comparison (#2 in Table 4) will be performed at α level of 0.01 based on patients randomized on or before 17 January 2021 in the mFAS. If the comparison is positive, this analysis will be considered as the final analysis of the proportion of patients with \geq 1 COVID-19-related hospitalization or all-cause death through day 29 for the 1200 mg group versus placebo comparison. Final analysis of the primary and key endpoints for the comparisons 3 to 10 (Table 4) will be performed based on

patients randomized on or before 17 January 2021 in the mFAS in the hierarchical order above at α level of 0.05.

If the interim analysis of the primary efficacy endpoint for the 1200 mg group versus placebo comparison (#2 in Table 4) is negative at α level of 0.01, no tests will be performed for the primary and key endpoints for the comparisons 3 to 10 in Table 4 based on patients randomized on or before 17 January 2021. Final analysis of the proportion of patients with \geq 1 COVID-19-related hospitalization or all-cause death through day 29 for the 1200 mg group versus placebo comparison (#2 in Table 4) and other comparisons 3 to 10 will be performed based on all patients randomized on or before 24 February 2021 and tested hierarchically at an alpha level adjusted based on the information fraction at the interim analysis using Gamma family alpha spending function, e.g., at 0.047 level as illustrated in the example in Table 5. Additional details are provided in section 7.

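### If the 1200 mg interim is negative, is it a fault that the 2400 mg primary result is not also specified on the 24 February data set?

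*Protocol*

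**What the plan says.** Protocol 11.2 fixes the 2400 mg analysis in time, with a cut-off early in 2021: "final primary efficacy analysis for the 2400 mg dose group versus placebo comparison will be performed based on patients randomized on or before 17 January". SAP 5.7.3 says the same of the primary endpoint: the "comparison will be performed based on patients randomized on or before 17 January 2021 in the mFAS", at a two-sided 0.05. SAP 1 gives the reasons, which are the data monitoring committee's advice to stop placebo for clear efficacy and a judgement that power was sufficient.

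The 1200 mg primary comparison has an interim look at 0.01 on the same date. If that look is negative, protocol 11.4.4 tests nothing further on the 17 January set. Comparison 2 (1200 mg, primary endpoint) and "other comparisons 3 to 10 will be performed based on all patients randomized on or before 24 February 2021", at an adjusted level illustrated as 0.047. Protocol Table 14 and SAP Table 4 list the 2400 mg items among comparisons 3 to 10:

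- 3 and 4: the primary endpoint in the high viral load and seronegative subgroups.
- 7: "death from day 4 through day 29 in the mFAS for REGN10933+REGN10987 2400 mg group versus placebo".
- 9: time to symptom resolution.

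The restriction to concurrent patients is written for the lower dose only (SAP 3.1): "For the analyses of 1200 mg group comparing to placebo, only patients concurrently randomized". Protocol Table 12 and SAP Table 2 carry a 24 February analysis row for 1200 mg but none for 2400 mg.

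**The concern.** In this branch the 2400 mg results would rest on two different sets of patients. The overall primary result would come from the 17 January set. The two subgroup results and the day 4 to 29 version would come from a larger set for which no overall 2400 mg versus placebo result is specified. A subgroup estimate is normally read beside the overall estimate in the same patients. A day 4 to 29 endpoint could also show more events than the through-day-29 endpoint that contains it, simply because its denominator is larger.

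The branch is not rare, and the 2400 mg set on 24 February has no row in either sample-size table. At stake would be the coherence of the 2400 mg results, and some precision left unused.

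**Working it through.** **Inputs** (protocol 11.2 and Table 12; SAP 2.2 and Table 2), mFAS per arm: 550 before amendment 6; 698 under amendments 6/7 by 17 January; 1122 under amendments 6/7 by 24 February. Event rates are 3.4% on placebo and 1.7% on treatment (50% reduction), or 1.36% (60% reduction).

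**The plan's own figure.** Power = Φ{[|p0 − p1|√n − 1.96√(2p̄(1 − p̄))] / √[p0(1 − p0) + p1(1 − p1)]}. With n = 550 + 698 = 1248 and p̄ = 0.0255, this is Φ{(0.6006 − 0.4369)/0.2226} = 76.9%, against the stated 76%. The same formula at n = 1122 gives 72.4%, against 72%.

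**Why the 1200 mg final analysis waits.** At 0.01 with 698 per arm, power is about 29%. A negative interim is therefore an expected outcome.

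**Size of the 24 February set for 2400 mg.** 550 + 1122 = 1672 per arm, which is 1122 − 698 = 424 more than for comparison 1. If only amendment 6/7 patients were meant, it would be 1122.

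**Events and precision.** Expected events at a 50% reduction are 1248 × (0.034 + 0.017) = 63.6 and 1672 × 0.051 = 85.3. With SE(log RR) = √[(1 − p0)/(np0) + (1 − p1)/(np1)], the expected 95% intervals are:

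| Reduction | n = 1248 | n = 1672 |
|---|---|---|
| 50% | 0.30 to 0.84 | 0.32 to 0.78 |
| 60% | 0.23 to 0.70 | 0.25 to 0.65 |

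**How often, and how much.** These are simulated trials with binomial events in blocks of 550, 698 and 424 per arm, a shared placebo group and pooled z-tests. Comparison 1 is tested at 0.05; comparison 2 at 0.01, then 0.047.

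| | 50% | 60% |
|---|---|---|
| Comparison 1 positive, 1200 mg interim negative | 53% | 47% |
| …and comparison 2 then positive, so comparison 3 is reached | 35% | 38% |
| Among those: median change in the 2400 mg risk ratio, 1672 versus 1248 | 0.039 | 0.038 |
| Among those: 2400 mg result on 1672 still has p < 0.05 | 98.9% | 99.7% |
| Among those: change exceeds the half-width of the expected 17 January interval (log scale) | about 0.1% | about 0.1% |

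A change of 0.05 or more in the risk ratio occurs in 41% (50% reduction) or 38% (60%) of trials in the branch. That threshold lies well inside sampling error: the expected 17 January interval is 0.84 − 0.30 = 0.54 wide at a 50% reduction and 0.70 − 0.23 = 0.47 wide at 60%.

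**Where the later patients appear.** The 424 later placebo patients per arm enter comparison 2, which is the same endpoint on the 24 February set. The 424 later 2400 mg patients enter the planned 1200 mg versus 2400 mg risk difference for the proportion endpoints (protocol 11.4.3.2; SAP 5.7.2), which covers mFAS patients under amendments 6, 7 and 8. Only the direct 2400 mg versus placebo contrast is unlisted.

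**Whether the plan prevents it.** The 17 January date belongs to the confirmatory analysis of comparison 1. The mFAS definition has no date limit. SAP 5.7.1 adds "Sensitivity analyses will be performed using FAS" and SAP 5.7.2 adds "Analyses will be performed for the cumulative incidence of patients having a COVID-19-related hospitalization or all-cause death through day 29", the latter with a 2400 mg versus placebo model. Neither states a cut-off, so either can be produced on the later set.

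**The case for a change.** The strongest case for a change is that comparisons 3, 4 and 7 are alpha-controlled tests on a set for which the tables give no 2400 mg size. A programmer might hesitate between 1672 and 1122 per arm, and SAP 1 links 24 February with the 1200 mg comparisons and 17 January with 2400 mg. The undated supportive analyses could be run on either set, so they do not guarantee the missing estimate. The remedy would cost a sentence and a table row.

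Part of this stands. The tables are incomplete, and no text orders the estimate. But Tables 12 and 2 give estimated sizes; they do not define analysis sets. The definitions limit concurrency for 1200 mg only, and protocol 11.4.4 speaks of all patients randomized by the later date, so the text resolves to 1672. Pre-amendment 6 patients on 2400 mg have placebo patients randomized alongside them, so including them breaks no concurrency.

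Comparisons 3, 4 and 7 each carry their own placebo group and can be interpreted without a matching overall estimate. A higher event count for comparison 7 would reflect its denominator; proportions and risk ratios are what the plan reports.

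**Conclusion.** No change follows. Followed as written, the plan gives a valid confirmatory result for 2400 mg on 17 January and valid hierarchical tests on 24 February. An estimate on the larger set would carry no alpha and could not replace the 17 January result. It would narrow the expected interval only from 0.30–0.84 to 0.32–0.78 at a 50% reduction, and would rarely change the reading. The gap is one descriptive output and one table row, in one branch of the testing scheme, and an analyst preparing the 24 February tables can sensibly supply both.

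This rests on the plan's event rates, on equal effects of the two doses, and on 1672 per arm, which is derived from Table 12 and not stated. If 1122 were meant, the later set would be smaller than 1248, and the points about a larger set and unused precision would fall away. The protocol reports results for both doses in section 3.3.1 but does not say which branch was taken.
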